Activities (see protocol below for detailed outline) include: **Introductory Forest Walk:** A guided forest walk will be conducted to control for effects of nature alone; **Wildlife Immersion Activity I:** Participants will experience wildlife through a wildlife rehabilitation setting in which they engage in activities such as feeding baby animals and enrichment; **Wildlife Immersion Activity II:** Participants will experience wildlife through observation of iconic wildlife at a wildlife park/ sanctuary and accompanying game keepers during feeding/enrichment; and **Wildlife Immersion Activity III:** Participants will experience wildlife in the natural setting through bird feeding and watching. This activity is designed to transition to a sustainable home activity that veterans can continue following study conclusion. After an initial training at Mass Audubon we will provide individual bird feeders to participants as well as community bird feeders at the indicated Soldier On facilities. Bird identification education and books will be provided. All settings also have self-guided educational displays so free time will be included in each session to facilitate each participant's transcendent inquiry as part of the wildlife immersion experience. The time between each set of activities will be spaced by at least one week as a washout period to reduce any carryover effect.³⁷ We anticipate that the forest walk will show a small improvement over baseline measures at enrollment (due to nature effect) and that each animal activity will show an additional improvement above the forest walk (nature plus animal).

INVESTIGATOR STUDY PLAN - REQUIRED**Intervention Protocol (to be refined with Advisory Committee)**

**Physiological = physiological measures (heart rate)*

Instruments = (Warwick-Edinburgh Mental-Well Being Scale, Speilberger State/Trait Anxiety Inventory, CES-D-10; NR-6; Human-Wildlife Bridging Feelings of Valuation Scale; and activity evaluation survey).

| | Location | Education | Activities | Animals Involved | Pre-Measure* | Post-Measure* |
|---|-----------------------------|---|--|---|---|--|
| Screening | | | | | Inclusion Criteria | |
| | | | | | 30-45 minutes | |
| Baseline | | | | | -PCL-5 -Consent -Demographics -Physio - -Instruments | |
| Time estimate | | | | | 1 hour | |
| Introductory Forest walk | | | | | | |

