| Time 1 | Harvard Forest | Forest overview/ ecology | Forest walk | Non-animal intervention | -Heart rate | -Heart rate -Instruments Post activity survey |
| Time estimate | 2 hour drive each way | 30 min. | 1 hour Followed by lunch | | 5 min. | 30 min. |
| Time 2 | Harvard Forest | Native trees | Forest walk | Non-animal intervention | -Heart rate | -Heart rate Instruments -Post activity survey |
| Time estimate | 2 hour drive each way | 30 min. | 1 hour Followed by lunch | | 10 min. | 30 min. |
| Wildlife immersion activity I: Wildlife rehabilitation | | | | | | |
| Time 1 | New England Wildlife Center | -Facility overview -Wildlife rehabilitation principles | -Feeding baby animals* -Enrichment activities -Wildlife care *expert-guided activities integrated with routine | Birds and small mammals such as squirrels | -Heart rate | -Heart rate -Instruments -Post activity survey |

INVESTIGATOR STUDY PLAN - REQUIRED

| | | | | | | |
|---|---------------------------------|--------------------------------------|---|---|------------------|--|
| | | | care so not to cause extra animal stress | | | |
| Time Estimate | 2 and ½ hour drive each way | 1 hour | 1 ½- 2 hours Followed by lunch | | 5 min. | 30 min. |
| Time 2 | New England Wildlife Center | -Human-wildlife interaction | As above | Birds and small mammals such as squirrels* | -Heart rate | -Heart rate Instruments -Post activity survey |
| Time Estimate | 2 and ½ hour drive each way | 1 hour | 1 ½-2 hours Followed by lunch | | 10 min. | 30 min. |
| Wildlife immersion activity II: Wildlife Observation | | | | | | |
| Time 1 | Maine Wildlife Park | -Sanctuary overview -Species info | -Observation -Accompany gamekeepers during feeding | 30 species for observation (including moose, deer, bobcats, fox, owls, skunks, porcupine) | -Heart rate | -Heart rate -Animal journal -Instruments -Post activity survey |
| Time Estimate | 4 hour drive each way | 1 hour | 2-3 hours Followed by lunch | | . 5 min. | 45 min. |
| Time 2 | Maine Wildlife Park | -Animal Enrichment | -Observation -Accompany gamekeepers during enrichment -Individual animal observation exercise | 30 species for observation (as above) | - -Heart rate | -Heart rate - Instruments -Animal journal (App. G) -Post activity survey |
| Time Estimate | 4 hour drive each way | 1 hour | 2-3 hours Followed by lunch | | 10 min. | 45 min. |
| Wildlife Immersion Activity III: Bird feeding/watching | | | | | | |

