| Time 1 | Mass Audubon Broad Meadow Brook | -Bird identification and feeding | -Nature walk with focus on identifying native bird species | -Birds | -Heart rate | -Heart rate -Instruments -Post activity survey |

INVESTIGATOR STUDY PLAN - REQUIRED

| Time Estimate | 1 ¾ hour drive each way | 1 hour | 1 hour | | 5 min. | 30 min. |
|---------------|---|---|--|--------|-------------|---|
| Time 2 | At Soldier On Facilities (with Mass Audubon specialist) | -Bird feeding F/U -Birds of prey -Citizen scientist | -Observing birds at feeder -Observing birds of prey (with specialist) | -Birds | -Heart rate | -Heart rate -Instruments -PCL-5 -Post activity survey -Focus group (study conclusion) |
| Time Estimate | At Soldier On | 1 hour | 1 hour | | 10 min. | 1- 1 ½ hours |
| Post study | Home bird feeding | | | | | -F/U interview/ phone call 4-6 weeks after final study activity |
| Time Estimate | | | | | | 15-20 min. |
| Time Estimate | | | | | | |
| Time Estimate | 8 weeks total; estimate of 10-15 minutes per day | | | | | |
| | | | | | | |

**Specific animals will be determined based on facility census and care routine.*

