We will utilize both quantitative and qualitative measures to assess parameters from study aims guided by a unitary-transformative paradigm of integrated bio-psycho-social-spiritual human needs.^{41,42}

Aim I: Feasibility and safety of intervention will be monitored through ongoing observation and safety logs and monitoring of recruitment/ retention. Acceptability will be assessed with evaluation surveys after each activity, focus groups at study conclusion and a follow-up phone/ in-person interview to assess bird feeder use 4-6 weeks after final study activity. The activity and focus group questions will be framed using transcendental method, a cognitive approach developed by the PI and used in several prior studies.⁴³

Aim II: Psychological measures will be conducted at baseline and after each activity to reduce learning effects. Psychological well-being will be assessed through Warwick-Edinburgh Mental-Well Being Scale (14 item; $\alpha=.91$)^{44, 45}, Speilberger State/Trait Anxiety Inventory (6 item; $\alpha=.82$)⁴⁶ and Center for Epidemiologic Studies Depression (CES-D-10) scale (10 item; $\alpha=.70$).⁴⁷ We will also measure physiological parameters. Heart_rate via wearable wrist biosensor will be measured at baseline and before and 5 minutes after each activity. Noninvasive stress markers such as heart rate are preferable as they reduce stress induced by collection and are more applicable in the field⁴⁹ as well as being consistent with a nature-focused intervention. We will also obtain a measure of PTSD symptoms through administering the PCL-5 at baseline and at study conclusion.^{23, 24}

Aim III: Connection to nature and wildlife will be measured with the short-form Nature-Relatedness (NR-6) (6 item; $\alpha=.85-.96$)⁵⁰ and Transcendent Feelings of Animal Valuation Scale developed by PI (7 item; $\alpha=.84-.94$)²⁰ at baseline and after each activity. Qualitative assessment will include an animal observation journal exercise during the Maine Wildlife Park activities.

Data management

INVESTIGATOR STUDY PLAN - REQUIRED

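### Heart rate is read 5 minutes after each activity with no stated seated rest, so exertion from the comparator walk can pass for a calming effect of the less active animal sessions

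*Combined protocol and SAP*

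**What the plan says.** Section 13 (Measures, Aim II) takes heart rate from a wrist sensor, "measured at baseline and before and 5 minutes after each activity", and presents it as a stress marker: "Noninvasive stress markers such as heart rate are preferable as they reduce stress induced by collection". The Objectives also name heart rate variability, but heart rate is the only physiologic Aim 2 outcome whose collection is described.

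Section 11 sets the comparator's role: "A guided forest walk will be conducted to control for effects of nature alone". The Intervention Protocol table gives the walk as "1 hour Followed by lunch" at both visits. Section 11 expects every animal activity to improve on the walk, and that extra improvement is meant to be the animal effect.

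The same table lists Activity I as "Feeding baby animals* -Enrichment activities -Wildlife care". Activity III Time 1 is a one-hour "Nature walk with focus on identifying native bird species". Activity III Time 2, held at the residence, includes "Observing birds at feeder" and watching birds of prey. Activity II is two to three hours at a wildlife park, observing and accompanying gamekeepers.

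Section 13 (Statistical analyses, Aim 2) compares outcomes across activities and baseline in a linear mixed model. It also estimates novelty for each activity from the difference in physiologic outcomes between its first and second session.

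**The concern.** Heart rate responds to physical effort as well as to stress. If it has not settled 5 minutes after an hour's walk, the walk's reading sits higher for a reason unrelated to animals or calm. A session with less walking then shows a lower reading than the comparator even if animals do nothing. Because a lower reading counts as less stress, the error runs in the direction the plan hopes to see.

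Two stated analyses are exposed: the contrast of the less active animal sessions with the forest walk, and the heart-rate novelty estimate for Activity III. Section 13 says that preliminary effect sizes and novelty effects will help choose the activities for the next trial, so the distortion could be carried forward. It is systematic, so more participants would not reduce it.

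**Working it through.** **1. Which contrasts are exposed.** By the content listed in Section 11:
- Forest walk, both visits: one hour of walking.
- Activity I, both visits: animal feeding, enrichment and care, with no walk listed. Probably less walking than the comparator, but not documented as stationary.
- Activity II, both visits: walking load not stated, so the direction is unknown.
- Activity III Time 1: a one-hour walk, roughly matched to the comparator in exertion.
- Activity III Time 2: watching birds on site, the clearest low-exertion session.

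**2. Whether anything in the plan separates exertion from the effect of interest.**
- The pre-activity reading captures the state on arrival, not effort during the session.
- Section 27 gives participants somewhere to sit while they write, but sets no rest before the reading.
- Section 22 (Privacy) describes reading the wrist monitor and sets no posture.
- The Aim 2 model names no exertion term.
- Table 1 in Section 13 lists nature and novelty as confounders, but not exertion.

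**3. The plan's own yardstick.** Section 13 states a detectable between-activity difference of 0.56 SD, with 36 effective participants, 80% power and Bonferroni correction for 6 comparisons.
- Effective n: 40 / (1 + 0.0105 × 9) = 40 / 1.0945 = 36.5, stated as 36.
- Normal formula: (z for two-sided 0.05/6 + z for 80% power) / √36 = 0.58 SD. The t version gives 0.61 SD.
- A value of 0.56 appears with the t version at two-sided 0.05/3.

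That discrepancy is a separate matter. I use the stated 0.56 only for scale.

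**4. In beats per minute.** The documents give no heart-rate figures. Assume an SD of the within-person difference of 8 to 12 bpm. Then 0.56 × 8 = 4.5 bpm and 0.56 × 12 = 6.7 bpm.

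**5. Chance of a spurious finding.** Let b be the assumed residual exertion in bpm, present after the walk and absent after the animal session, with no true animal effect. The bias is b / SD. The chance of a significant result favouring the animal session comes from the noncentral t with n = 36. In each range, the first value is for SD 12 and the second for SD 8.

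| b (bpm) | Bias (SD) | At two-sided 0.05/6 | At two-sided 0.05 |
|---|---|---|---|
| 1 | 0.08 to 0.13 | 1.5% to 2.7% | 7% to 11% |
| 2 | 0.17 to 0.25 | 5% to 11% | 16% to 31% |
| 3 | 0.25 to 0.38 | 11% to 31% | 31% to 59% |
| 5 | 0.42 to 0.63 | 40% to 82% | 68% to 95% |

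For reference, with no bias the chance in this one direction is 0.4% at 0.05/6 and 2.5% at 0.05.

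**6. Novelty in Activity III.** Time 1 minus Time 2 is walking minus watching, so it carries the whole of b. In the other activities the listed content is the same or similar at both visits, so this problem does not clearly arise.

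**The case against.** The strongest reply is that the effect may be negligible. The only indication of pace is the eligibility criterion in Section 6, a mile or less at a leisurely pace, and five minutes may be enough to recover from that. Seating is planned for the written measures. Heart rate is one of several secondary outcomes in a feasibility pilot, and Section 13 itself warns that pilots estimate between-condition effects poorly. Activity selection will also draw on retention, expert opinion and the literature.

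Much of this stands. The size rests on assumed inputs, and at 1 bpm there is little to correct. Pooling the two Activity III sessions would roughly halve the bias for that activity, because only Time 2 differs from the walk: 5 bpm becomes about 2.5 bpm. What does not stand is the idea that the plan already deals with the problem. A seat for writing is not a rest before the reading, and no planned reading would show whether the residual is 1 bpm or 5 bpm.

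A reader might also infer several stronger points that the documents do not support:
- That all the animal activities are favoured. Activity III Time 1 is itself a walk, and Activity II's walking load is unknown.
- That Activity I is stationary. The documents only omit a walk from its listed tasks.
- That heart rate is the study's only objective endpoint. Recruitment, retention and safety incidents are Aim 1 outcomes.
- That the 0.48 SD figure in Section 13 is a suitable yardstick. It is for comparisons with baseline, without multiplicity correction.

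**Conclusion.** The point holds as a cheap improvement to a secondary outcome. As written, the heart-rate contrast between the forest walk and the less active animal sessions cannot separate calm from recovery after walking. The Activity III novelty estimate cannot separate novelty from exertion. The case is clearest for Activity III Time 2 and plausible for Activity I.

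The size is unknown and may be small. It matters if the residual at 5 minutes reaches about 3 to 5 bpm, given an SD of 8 to 12 bpm; both are assumptions. It would be going too far to say that heart rate will decide the ranking of activities, or that the bias is large. The primary Aim 1 outcomes and the questionnaires do not depend on the heart-rate reading.

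**What to change.** - Take the pre-activity reading after a few minutes seated, within the 5 to 10 minutes already allotted.
- Keep the 5-minute post-activity reading and label it descriptive.
- Add a second reading from the same device after a fixed seated interval, for example 15 to 20 minutes, identical in all eight sessions and taken during the survey block.
- Take it before lunch in every session. In the final session, also take it before the PCL-5 and focus group. That session's post-activity block runs 1 to 1½ hours, against 30 to 45 minutes elsewhere, and Section 14 recognises that the PCL-5 may itself provoke symptoms. A reading at the end of each block would therefore bring in a new bias in the very session of most interest.
- Use the rested reading for the between-activity, activity-versus-walk and novelty contrasts.

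The cost is one more reading per session, with no extra visit or equipment. The order of surveys and lunch must be held constant; the activity table lists lunch for the forest walk and Activities I and II but not for Activity III, while the risk table in Section 16 provides one each day. A very brief effect would show only in the 5-minute reading, which is kept.

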Surveys with ID numbers will be conducted using pen and paper and collected by PI immediately afterwards. Quantitative data will be entered into SPSS version 24 by research assistant and/or PI using double data entry. Focus group audiotapes will be transcribed by a transcriptionist using Microsoft word files. All data will be stored in a password-protected institutional research drive with access limited to investigators and research assistant. Hard copies will be kept in locked file/office.

Analytic Plan

Sample size and power: Because pilot studies do not provide meaningful estimates of effect sizes for between-condition comparisons, due to the imprecision inherent in small samples^{51,52} we base our proposed sample size of 50 participants – anticipated average of 10 per group – on pragmatics of recruitment, retention, and examination of feasibility, acceptability, and safety, providing important information for planning a future R01 study. Taking retention as an illustrative Aim 1 outcome, a 95% confidence interval is (35.5%, 64.5%) for a rate as low as 50% seen in the PTSD literature,² and (66.3%, 90.0%) for 80% retention. [name] (Co-I) has a long standing relationship of working with Soldier On and has obtained follow up rates above 80% in other studies.⁵³ For Aim 2-3 analyses, we adjust the sample size for possible within-group correlation (intra-class correlation, ICC) using $ICC=0.0105$ from a prior study of mindfulness.⁵⁴ Applying the resulting design effect⁵⁵ of $1+0.0105 \times (10-1)=1.0945$ and 80% retention rate yields an effective sample size of $40/1.0945=36$ participants. With an overall 0.05 Type I error rate and a Bonferroni correction for multiple testing (6 pairwise comparisons of the 4 activities), and 80% power, we will be able to detect a statistically significant mean within-participant between-activity difference in an outcome, e.g., anxiety, of 0.56 SD, where SD indicates standard deviation of within-participant change in the outcome. The corresponding detectable within-participant change from baseline to end of study or baseline versus each individual activity (no corrections for multiple testing), is 0.48 SD.

Statistical analyses:

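### The only multiplicity rule on record for the six between-activity comparisons is single-step Bonferroni; a step-down rule at the same overall 0.05 rejects at least as much, and the analysis section should name one

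*Combined protocol and SAP*

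**What the plan says.** Section 13, Analytic Plan, Sample size and power, gives the planning basis for the Aim 2 and Aim 3 comparisons. It reads "With an overall 0.05 Type I error rate", then names a "Bonferroni correction for multiple testing (6 pairwise comparisons of the 4 activities") with 80% power, and concludes that a between-activity difference of 0.56 SD of within-participant change is detectable. For change from baseline it gives a second figure: "baseline versus each individual activity (no corrections for multiple testing), is 0.48 SD". Both rest on the statement that an "80% retention rate yields an effective sample size of $40/1.0945=36$ participants".

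Under Statistical analyses, Aim 2 specifies a linear mixed model comparing outcomes across activities and baseline, and Aim 3 runs in parallel. Neither names a multiplicity procedure.

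Section 11 gives the expected pattern: a small gain after the forest walk, and then "each animal activity will show an additional improvement above the forest walk". Section 10 makes the Aim 2 and Aim 3 measures secondary. The sample size is pragmatic: "we base our proposed sample size of 50 participants" on recruitment, retention and feasibility grounds.

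**The concern.** All six pairwise differences among four means are in the family, and these hypotheses are logically linked. If any one pair of means differs, at most three of the remaining equalities can still be true (three means equal, one apart). Bonferroni still divides by six at every step. Step-down procedures use the link, or simply the count of hypotheses not yet rejected, and keep the same familywise guarantee.

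What is at stake is how many of the wildlife-versus-walk contrasts can be declared once one has been. Section 4 aims to assess the relative efficacy of the three interventions, and Section 13 says the results will inform which activities go into the later study. Because the analysis text is silent, the analyst would either inherit Bonferroni from the power paragraph or choose a rule after seeing the data.

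**Working it through.** **Inputs.** Overall error rate 0.05, six comparisons, 80% power, design effect 1 + 0.0105 × 9 = 1.0945, and 40/1.0945 = 36.5, stated as 36 (all Section 13). The SD is that of the within-participant difference, so each contrast is treated as a one-sample t-test with SD 1 and 35 degrees of freedom. Sidedness is not stated.

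**1. Reproducing the plan's figures.** Power is taken from the noncentral t distribution with noncentrality d√36 = 6d.
- Unadjusted, two-sided 0.05: critical t = 2.030, and 80% power needs d = 0.480. This matches the plan's 0.48. One-sided 0.05 would give 0.42, so the plan's basis is evidently two-sided.
- Bonferroni, two-sided 0.05/6 = 0.00833: critical t = 2.797, and 80% power needs d = 0.61, not 0.56. At d = 0.56 (noncentrality 3.36) power is 71.0%. About 43 effective participants would be needed for 80%.
- Normal approximation: (2.638 + 0.842)/6 = 0.58, with power 76.5% at 0.56. This also misses 0.56.
- The figure 0.5625 appears with two-sided 0.05/3, which is the same as one-sided 0.05/6. That conflicts with the two-sided basis of 0.48.

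**2. Divisors.** With four means, the number of equalities that can be true together is 6 (all equal), 3 (three equal, one apart), 2 (two pairs), 1 (one pair) or 0. The largest value still possible after 0, 1, 2, 3, 4 and 5 rejections gives Shaffer's divisors 6, 3, 3, 3, 2, 1. Holm uses 6, 5, 4, 3, 2, 1; Bonferroni uses 6 throughout. No step-down divisor exceeds 6, so every Bonferroni rejection is also a Holm and a Shaffer rejection. The first divisor is 6 in all three, so the chance of rejecting at least one hypothesis is identical.

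**3. Size of the gain.** Simulation with n = 36, normal data, every pairwise difference with SD 1 (an assumption) and two-sided paired t-tests. The pattern (0, d, d, d) is the walk followed by three equal wildlife activities.

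| True means (SD units) | Quantity | Bonferroni | Holm | Shaffer |
|---|---|---|---|---|
| 0, .56, .56, .56 | power per true contrast | 71.1% | 74.3% | 77.9% |
| | all three true contrasts | 47.6% | 54.7% | 59.8% |
| | at least one true contrast | 91.2% | 91.2% | 91.2% |
| | familywise error | 2.5% | 3.6% | 4.5% |
| 0, 0, .56, .56 | average power per true contrast | 70.7% | 76.2% | 78.3% |
| 0, .56, 1.12, 1.68 | average power per true contrast | 85.5% | 94.7% | 94.7% |
| 0, .30, .30, .30 | power per true contrast | 17.7% | 18.8% | 21.0% |

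In the expected pattern, 80% power per contrast needs about 0.61 SD (Bonferroni), 0.59 to 0.60 (Holm) or 0.57 to 0.58 (Shaffer).

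**4. Closer to the mixed model.** Pooling the error variance across activities raises all three figures in the first pattern to about 75%, 78% and 81% per contrast. The ordering and the approximate gain remain.

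**The case against.** The strongest objection is that Bonferroni is only a planning input. It appears once, in the power paragraph, and the analysis text commits to nothing. That stands: a reader might infer that the plan will test each contrast at 0.05/6, but the documents do not say so. The supportable point is that the only rule on record is the less powerful one and that the analysis text should name a rule.

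Three further readings go too far.
- *Step-down testing is free.* It is not quite. Bonferroni has simple matching simultaneous intervals and step-down decisions do not, which matters in a pilot meant to yield estimates. The extra power also comes from using slack in the error rate (2.5% against 4.5% in the first pattern), although both stay within 0.05.
- *The expected pattern is where the gain is greatest.* It is not. Gains at 0.56 SD are larger when more pairs differ. Section 11 also does not say that the three wildlife activities are equal; that is an assumption of the calculation.
- *Step-down testing restores the planned 80% at 0.56 SD.* On the paired-t basis it does not: Shaffer reaches about 78%.

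It can also be said that little depends on this. The outcomes are secondary, the analyses are described as preliminary, and the sample was not set by power. The activity order is fixed, so more rejections do not make the contrasts easier to interpret. All of this stands and sets the priority. Nor does a rule for these six contrasts address multiplicity across the several Aim 2 and Aim 3 outcomes, on which the documents are silent.

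**Conclusion.** The point holds as a low-priority improvement. That Shaffer's or Holm's procedure rejects everything Bonferroni rejects at the same overall 0.05 follows from the procedures and does not depend on simulation. The size of the gain does depend on assumptions. With 36 effective participants, equal SDs of differences and three equal effects of 0.56 SD, it is about 3 points (Holm) or 7 points (Shaffer) per contrast, and about 7 or 12 points for showing all three. It is about 1 to 3 points when the effects are 0.30 SD.

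Separately, the 0.56 SD and 0.48 SD figures do not share a basis. Given the two-sided t-test behind 0.48, the first should be about 0.61 SD. This does not show that 50 participants is the wrong number, since the plan does not derive its sample size from power.

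**What to change.** In Section 13, under both Sample size and power and the Aim 2 and Aim 3 analyses, state that within each outcome the six between-activity contrasts from the mixed model are tested with Shaffer's step-down procedure for all pairwise comparisons (or Holm's) at an overall two-sided 0.05. Report each estimate with a confidence interval labelled as unadjusted or Bonferroni-adjusted, and note that an unadjusted interval may exclude zero when the step-down test does not reject.

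In the same edit, state the sidedness and correct the detectable difference for 0.05/6 from 0.56 to about 0.61 SD (0.58 if the normal approximation is intended, in which case 0.48 becomes 0.47 on the same basis). The Bonferroni figure can stay as a conservative planning value.

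The cost is a sentence or two of text and a few lines of code, with no additional participants or data. The one real downside is the lack of simple simultaneous intervals that match the test decisions.

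### The detectable between-activity difference of 0.56 SD does not follow from its stated inputs: six Bonferroni comparisons at an effective n of 36 give about 0.61 SD, and power at 0.56 SD is about 71%, not 80%

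*Combined protocol and SAP*

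**What the plan says.** All the inputs stand in one paragraph of Section 13, Analytic Plan, Sample size and power.

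- Enrolment is set at "our proposed sample size of 50 participants – anticipated average of 10 per group". With 80% retention and a design effect of 1.0945, the effective sample is given as 36.
- The error rate is described as "With an overall 0.05 Type I error rate", with "a Bonferroni correction for multiple testing (6 pairwise comparisons of the 4 activities), and 80% power".
- The conclusion is that "we will be able to detect a statistically significant mean within-participant between-activity difference in an outcome, e.g., anxiety, of 0.56 SD". The SD is defined as that of the within-participant change.
- A companion figure covers change from baseline to the end of the study and "baseline versus each individual activity (no corrections for multiple testing), is 0.48 SD".

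The paragraph states neither the test nor whether it is one- or two-sided.

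**The concern.** The two detectable differences are presented as a pair from the same effective sample, differing only in the multiplicity correction. Dividing 0.05 by six should raise the detectable difference by more than the step from 0.48 to 0.56 SD.

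This is the only sensitivity the plan gives for comparing activities with one another. Aim 2 includes judging the relative efficacy of the three interventions, and the Aim 3 analyses run in parallel. A reader will use 0.56 SD to decide how much a null between-activity result means. If the figure is too small, such a result looks more informative than it is. The mismatch also leaves open whether six or three contrasts are meant, which changes the per-comparison threshold from 0.0083 to 0.0167.

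**Working it through.** **Inputs** (all from the Sample size and power paragraph): 50 enrolled; 80% retention; ICC 0.0105; groups of 10; overall alpha 0.05; six comparisons; 80% power; effect in units of the SD of within-participant change.

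**Effective sample size**
- Design effect: 1 + 0.0105 × (10 − 1) = 1.0945.
- Retained: 50 × 0.80 = 40.
- Effective n: 40 / 1.0945 = 36.55, which the plan takes as 36. This reproduces.

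**Method.** An effect in SDs of within-participant change implies a one-sample (paired) t-test on differences. For a standardised difference d, the noncentrality is d√n on n − 1 degrees of freedom. With n = 36, √n = 6 and df = 35. Two-sided power is P(T > t_crit), where T is noncentral t; the opposite tail is negligible.

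**Reproducing the plan's own 0.48 SD.** For two-sided alpha 0.05, t_crit = 2.030. Power reaches 80% at d = 0.480 (noncentrality 0.480 × 6 = 2.88). This matches. A one-sided test would give 0.42, and the normal approximation gives (1.960 + 0.842) / 6 = 0.467, so neither matches. The two-sided paired t-test is therefore the natural reading.

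**The same method with six comparisons**
- Alpha per comparison: 0.05 / 6 = 0.00833 two-sided; t_crit = 2.797.
- 80% power is reached at noncentrality 3.664, so d = 3.664 / 6 = **0.611 SD**.
- Ratio to the stated figure: 0.611 / 0.56 = 1.09.
- Power at 0.56 SD (noncentrality 0.56 × 6 = 3.36): **71.0%**.
- Effective n for 80% power at 0.56 SD: 43 (n = 42 gives 79.8%).

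**Other readings**

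| Reading | Detectable difference (SD) |
|---|---|
| Two-sided t, n = 36, six comparisons | 0.611 |
| Same, Šidák instead of Bonferroni | 0.609 |
| Two-sided t, n = 36.55 | 0.606 |
| Two-sided t, n = 37 | 0.601 |
| Pooled error df, 3 × 35 = 105, n = 36 | 0.590 |
| Normal approximation, n = 36: (2.638 + 0.842) / 6 | 0.580 |
| Normal approximation, n = 36.55 | 0.576 |
| Two-sided t, n = 40 (design effect dropped) | 0.576 |
| Normal approximation, n = 37 | 0.572 |
| Normal approximation, n = 40 (design effect dropped) | 0.550 |
| One-sided t, n = 36, six comparisons | 0.5625 |
| Two-sided t, n = 36, **three** comparisons | 0.5625 |

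The one-sided row comes to 0.56, but the same convention gives 0.42 for the uncorrected figure. The three-comparison row gives 0.5625 alongside 0.480, so it matches both published figures (power at 0.56 SD is 79.6%). No single convention tried matches both figures with six comparisons.

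**The case against.** The strongest objection is that little depends on this number. The plan says that pilots do not give meaningful between-condition effect sizes, and it bases enrolment on practical and feasibility grounds. Aim 1 is primary, and the Aim 2 analyses are called preliminary. Correcting the figure changes no enrolment number, model or procedure. All of this stands. It limits the consequence, but the stated sensitivity is still wrong for the inputs beside it.

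The second objection is that the test is not stated and is inferred from a two-digit match, while the planned analysis is a linear mixed model rather than a set of paired t-tests. This partly stands. With pooled df of 105 the figure is 0.590 SD and power at 0.56 SD is about 75%; by the normal approximation they are 0.580 SD and 76.5%. The overstatement therefore ranges from about 4% (0.580 / 0.56 = 1.04) to 9%, depending on the method. But these alternatives give 0.47 rather than 0.48 for the companion figure, and neither yields 0.56.

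The third objection is that a divisor of three is conjecture. That is fair: a divisor of four with the normal approximation gives 0.557, and n = 40 with pooled df gives 0.559. Each departs from a stated input, so neither rescues the figure. How 0.56 arose is uncertain; that it does not follow from the stated inputs is not.

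**Conclusion.** The concern holds. With an effective n of 36, two-sided 0.05/6 and 80% power, the detectable between-activity difference is 0.61 SD, not 0.56 SD. At 0.56 SD power is about 71%, so the chance of missing such a difference is about 29% rather than 20%.

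These values assume the two-sided paired t-test, which is the one that reproduces the plan's 0.48 SD. Keeping n = 36 and six two-sided comparisons, the more favourable methods tried give 0.58 to 0.59 SD and about 75% to 77% power, still short of the claim. The error concerns the stated sensitivity for Aims 2 and 3. It does not affect the enrolment of 50 or the primary Aim 1 outcomes.

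**What to change.** In Section 13, Sample size and power, replace 0.56 SD with 0.61 SD for the six-comparison correction, and state that the calculation uses a two-sided paired t-test. If another method was used, name it and recompute both detectable differences with it.

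Alternatively, if only three contrasts were ever intended (for example each wildlife activity against the forest walk), say three comparisons, list them, keep 0.56 SD, and test at 0.05/3 in the analysis. This is justified only if it reflects the real intention, because the text now names all six pairs; the set of comparisons should not be narrowed merely to preserve the number.

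The cost of the first option is one figure, a clause naming the test, and a slightly less favourable stated sensitivity. No extra participants are needed.
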